#### **8.1.3. 24-Hour Total Sleep Time**

Electronic sleep diaries will be completed by the participant daily for approximately 7 days around the time of (and including) each 24-hour BP recording.

For each participant, weekly mean sleep time, weekly mean wake time, and daily and weekly total sleep time (TST) will be calculated.

Weekly mean sleep time and weekly mean wake time will be calculated as the mean of values reported in the participant sleep diary around and including each 24-hour BP recording. Times should be converted to 24-hour format (adding 24 to times denoted as AM; e.g., 1:20 AM = 25:20) and expressed in minutes (multiply hours by 60 and add minutes) to facilitate the calculation before calculating the means. After calculating the mean, convert the result back to a time by dividing the result by 60 and assigning the whole number to hours and the remainder multiplied by 60 to minutes (rounding to nearest whole number). If the number of hours is less than 24, express as PM; if the number of hours is greater than 24, subtract 24 and express as AM.

Daily TST is calculated as ((A – B) – (C + D)), where A is "Awake Time", B is "Sleep Time", C is "Minutes to Fall Asleep", and D is "Minutes Spend Awake" from the electronic diaries. Values

for Sleep Time and Awake Time may be converted to minutes as above to facilitate the calculation; Fall Asleep (C) and Spend Awake time (D) may then be subtracted and the TST result remains expressed in minutes.

Weekly mean TST will be calculated as the mean of daily TST values associated with each visit.

Weekly mean TST at each visit and change from baseline will be summarized as continuous variables. Daily and weekly mean sleep and wake times will be listed, with footnote denoting which values were used for calculating daytime/nighttime windows (see Section 7.2.2).

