### 7.2.1. Primary Analysis

The secondary efficacy endpoints will be summarized and analyzed using the Completer Set and methods described for the primary endpoint.

---

As the endpoint is only captured once during follow-up, including the constant-valued visit identifier (AVISITN) as a class covariate will not affect the model while permitting use of the LSMEANS statement to calculate the mean change in SBP.

Daytime and nighttime windows "are best defined using sleeping times reported by individual users' diary cards". Accordingly, day/night windows subdividing the 24-hour ABPM data will be defined using on sleep/wake times captured from participant sleep diary entries on the nights where the ABPM is being used. Sleep diary times may be converted to 12- or 24-hour format as necessary to merge with ABPM entries and perform the summaries. If valid sleep diary entries covering the ABPM night are not available but other diary entries for the visit are available, the weekly mean sleep/wake time (see Section 8.1.3) may be used to create the daytime/nighttime windows (Section 5.2.4).

A supporting analysis of the daytime/nighttime SBP endpoints will be performed using fixed time windows of 09:00h to 21:00h (daytime) and 01:00h to 06:00h (nighttime) for all participants. However, if the percentage of participants with non-missing sleep diary data is below 85% (N<37 at the interim analysis; N<49 to N<66 at the final analysis), then the fixed window analysis will be considered the primary analysis (including use for statistical testing hierarchy) and the diary-based analysis will be considered supportive.

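### SAP 8.1.3 does not carry a wake time at or after noon to the next day, so that night's total sleep time is negative and a fallback day/night boundary can be hours too early

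*SAP*

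**What the plan says.** SAP 8.1.3 gives one conversion for diary sleep and wake times. It puts times on a 24-hour clock and adjusts them by "adding 24 to times denoted as AM"; the SAP's example turns 1:20 AM into 25:20. The result is expressed in minutes. The mean is turned back into a clock time by "dividing the result by 60 and assigning the whole number to hours", with the remainder as minutes. The label depends on the hours. The first branch reads "If the number of hours is less than 24, express as PM". The second, for hours above 24, takes 24 off and labels the time AM.

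Daily TST is awake time minus sleep time (A - B), less the minutes taken to fall asleep (C) and the minutes spent awake (D). The SAP adds that the values "for Sleep Time and Awake Time may be converted to minutes as above to facilitate the calculation". It gives no other conversion for TST.

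The weekly means have a second use. Under SAP 7.2.1 (and 5.2.4), if there is no valid diary entry for the ABPM night but other entries for that visit exist, "the weekly mean sleep/wake time (see Section 8.1.3) may be used to create the daytime/nighttime windows". Those windows define daytime and nighttime average SBP, the second and fourth hypotheses in the testing order of SAP 5.4. They also define nocturnal dipping in SAP 7.3.2.

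Neither document gives a next-day rule for PM wake times or a check for negative TST.

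**The concern.** The conversion treats AM as meaning the next day and PM as meaning the evening before. That works for bedtimes on either side of midnight and for morning wakes. It fails for a wake time at or after noon, which is denoted PM but belongs to the next day. Two results can then be wrong: TST for that night, and the mean wake time for any week in which some wakes fall before noon and some after.

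The TST error affects a descriptive summary. The mean wake time matters more, because under the fallback it decides which ABPM readings count as night. Daytime SBP is the first secondary test, and failing it ends formal testing of the seated and nighttime endpoints, so its windows should rest on a rule that gives the right clock time.

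**Working it through.** **Inputs.** The conversion, back-conversion and TST formula are from SAP 8.1.3. That section also gives about 7 diary days per recording; this leaves about 6 if the ABPM-night entry is the missing one. ABPM reading intervals are from protocol 8.2.1. The clock times below are illustrative assumptions, as are C = 15 and D = 30 min where TST is shown. The sign of the result does not depend on C and D.

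**The SAP's own example and ordinary nights.** 1:20 AM becomes 25:20, or 25 × 60 + 20 = 1520 min, as stated. For 11:00 PM to 7:00 AM, A - B = 1860 - 1380 = 480 min. For 1:00 AM to 9:00 AM, A - B = 1980 - 1500 = 480 min. Both are correct.

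**TST with an afternoon wake.** 12:30 PM converts to 750 min; on the next-day scale it should be 750 + 1440 = 2190.

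| Sleep to wake | A - B as written | True A - B |
|---|---|---|
| 1:00 AM to 12:30 PM | 750 - 1500 = -750 min (-12.5 h) | 2190 - 1500 = 690 min (11.5 h) |
| 11:00 PM to 12:30 PM | 750 - 1380 = -630 min | 810 min |
| 2:00 AM to 12:30 PM | 750 - 1560 = -810 min | 630 min |

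In general, an overnight sleep of true length L < 1440 min that ends at or after noon is returned as L - 1440, which is always negative. One such night also affects the weekly mean. Take six nights of 11:00 PM to 7:00 AM (TST 480 - 45 = 435 min) and one of 2:00 AM to 12:30 PM. As written, the mean is (6 × 435 - 855)/7 = 251 min; the correct value is (6 × 435 + 585)/7 = 456 min.

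**Mean wake time.** With k wakes after noon among n days, the sum is short by 24k h, so the mean is 24k/n h too early. With wakes at 7:00 AM and 12:30 PM:

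| n | k | As written | Correct | Error |
|---|---|---|---|---|
| 7 | 1 | (6 × 1860 + 750)/7 = 1701 min = 28:21, 4:21 AM | (6 × 1860 + 2190)/7 = 1907 min = 31:47, 7:47 AM | 24/7 = 3.43 h |
| 7 | 2 | 25:43, 1:43 AM | 8:34 AM | 6.86 h |
| 7 | 3 | 23:04, labelled PM | 9:21 AM | 10.29 h |
| 6 | 1 | 27:55, 3:55 AM | 7:55 AM | 4.0 h |

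If every wake in the week is after noon, the mean clock time is correct (12:30 PM). The boundary error needs a mixed week.

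**Size on the ABPM scale.** An error of 3.43 h is 3.43 × 2 = about 7 readings at the 30-minute night interval, or 3.43 × 3 = about 10 at the 20-minute day interval, moved from night to day in one recording.

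**Hour 24, a separate matter.** Bedtimes of 11:30 PM, 11:59 PM, 12:15, 12:30, 12:45, 1:00 and 1:30 AM convert to 1410, 1439, 1455, 1470, 1485, 1500 and 1530 min. Their mean is 10289/7 = 1470 min, or 24:30. The whole-number hour is 24, which is neither below nor above 24, so no label is assigned.

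**The case against.** The strongest reply is that the error reaches little.

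- The usual path takes sleep and wake times from the ABPM night itself. The weekly mean is an optional fallback.
- Protocol 5.2 excludes night and variable shift workers, 5.3 asks for consistent sleeping habits, and 8.2.3 has sites pursue missing diary entries.
- A fixed-window analysis is run in any case, and becomes primary if diary data fall below 85%.
- Sleep and wake times are listed with a note of which set the windows, so a displaced boundary could be seen.
- The conversion for TST is worded as permissive, and a programmer working from date-times would avoid the error.

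Most of this stands, and it makes the point minor. It does not make the rule correct. The shift-work exclusion makes afternoon wakes less likely but does not rule them out. The SAP thresholds (37 of 43, 49 of 57, 66 of 77) leave diary windows primary with up to 6, 8 or 11 participants lacking diary data. The SAP does not ask for date-times.

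A reader might infer more than the text supports:

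- **That 12:20 AM becomes 36:20.** It does not. The SAP converts to 24-hour format first, so 12:20 AM is 00:20 and then 24:20.
- **That a mean bedtime just after midnight has no result, or that the hour-24 gap causes negative TST.** The mean in minutes exists; only its label is missing. If hours are read as a decimal, only exactly 24:00 is uncovered. The gap plays no part in the TST error.
- **That TST is wrong for everyone, or that the daytime and nighttime results are generally unreliable.** Nights ending before noon are handled correctly, and the windows are affected only when the fallback is used in a mixed week.

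**Conclusion.** The rule is wrong as written, with minor consequences. Any overnight sleep that ends at or after noon gets a TST exactly 1440 min too low, hence negative. In a week mixing wakes before and after noon, the mean wake time is 24k/n h too early: 3.4 h for one such day in seven, 4.0 h for one in six.

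The effect is limited to the descriptive TST summaries and, through the optional fallback, to the daytime and nighttime SBP windows and the dipping measure derived from them. The primary 24-hour average SBP does not use these windows.

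The sizes follow from the SAP's arithmetic applied to illustrative clock times. The documents give no frequency for afternoon wakes or for use of the fallback, so the number of participants affected is unknown and may be nil. The missing branch for hour 24 is a small labelling gap that the same edit can close.

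**What to change.** Keep the SAP's scale and add one condition in SAP 8.1.3:

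1. Convert to 24-hour format and add 24 h to AM times, stating that 12:xx AM becomes 24:xx.
2. If the converted wake time is earlier than that night's converted sleep time, add 24 h to the wake time.
3. Use these values for both the weekly means and TST.
4. Convert means back modulo 24 on a 24-hour clock, so that 24:30 becomes 00:30 and no AM/PM branch is needed.

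This gives 11.5 h for 1:00 AM to 12:30 PM and 7:47 AM for the seven-day example, and leaves ordinary nights unchanged (11:00 PM to 7:00 AM stays at 480 min; 1:00 AM to 7:00 AM is 1860 - 1500 = 360 min). Sleep and wake must share one origin. Measuring sleep from noon and wake from midnight would turn 11:00 PM to 7:00 AM into 1860 - 660 = 1200 min.

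Alternatively, compute both quantities directly from date-times, if the diary records them.

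The cost is a line or two of SAP text and the matching code. No new data or design change is needed.

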## 8.2. Adverse Events

AEs will be coded to system organ class (SOC) and preferred term using the Medical Dictionary for Regulatory Activities (MedDRA), Version 26.0 or later. The investigator will assess the relationship of each AE to study drug. AE with a missing relationship to study drug will be reported as related in the summaries. Severity, as determined by the Investigator using Common Terminology Criteria for Adverse Events (CTCAE) version 5.0 or higher, will be classed as mild, moderate, severe, life-threatening, or fatal. An AE with missing severity will be reported as missing in the summaries.

If a subject has multiple episodes of events coded to the same SOC or PT, then the subject will be counted just once in the summaries for that term. Subject incidence of AEs by SOC and PT tables are sorted by SOC (alphabetical order) and then by PTs (descending order) within each SOC for the overall frequency.

A general overall summary of AEs with the number and percent of subjects who experienced the following types of events will be provided:

- Subjects with any AE
- Subjects with AE by maximum severity
- Subjects with any AEs related to study intervention
- Subjects with any serious related AE
- Subjects with any AE leading to discontinuation
- Subjects with any AE leading to death

In addition, subject incidence of AEs will be summarized by following:

- SOC and PT
- Maximum severity by SOC and PT
- Treatment-related by SOC and PT
- AE leading to discontinuation by SOC and PT
- Serious AEs
- Fatal AEs

## 8.3. Laboratory Assessments

Results from clinical laboratory assessments described in the protocol will be summarized as continuous variables. Where included in laboratory reports, abnormally high/low or other clinically significant observations will be denoted in listings.

#### **8.4. Pregnancy**

Pregnancy results will be presented in listings only.

#### **8.5. Vital Signs**

Sitting heart rate, weight, and height at each visit, including change from baseline, will be summarized as continuous variables.

#### **8.6. 12-Lead Electrocardiogram (ECG)**

Machine-read ECG parameters at each visit and change from baseline will be summarized as continuous variables.

#### **8.7. Columbia-Suicide Severity Rating Scale (C-SSRS)**

C-SSRS responses and aggregated responses for suicidal ideation or suicidal behavior at screening will be summarized as categorical variables using the Safety Set.

### **9. PHARMACOKINETIC ANALYSES**

Not applicable.

### **10. PHARMACODYNAMIC ANALYSES**

Not applicable.

## 11. MODIFICATION HISTORY

Version	Date	Description
3.0	05 Dec 2024	
 
• Revisions to align with latest Protocol Amendments.
 
• Updated GMA signatory
 
• Corrected calculation of sleep diary NTST parameter
 
• Corrected reference for AE severity coding
 
• Removed comparison of PGI-S vs PGI-C
 
• Clarified presentation of Protocol Deviations
 
• Clarified O'Brien-Fleming and Pocock alpha levels as one-sided
 
• Clarified application of visit windows in table presentations
 
• Removed presentation of LS mean differences for subgroups
 

2.1	15 Feb 2024	
 
• Correction to modification history section.
 

2.0	13 Feb 2024	
 
• General updates to align with Protocol Amendment 2.
 
• Clerical and style updates.
 
• Revised fixed day/night windows to align with international guidance and added threshold for using fixed windows in analysis.
 
• Clarified IA procedure and provided GSD alpha levels.
 

1.0	05 Jul 2023	Initial version

**Table 1: List of Abbreviations**

Abbreviation	Term
AE	Adverse event
AEOSI	Adverse event of special interest
AHA	American Heart Association
ALT	Alanine transaminase
ABPM	Ambulatory blood pressure monitoring
AST	Aspartate aminotransferase
BP	Blood pressure
BUN	Blood urea nitrogen
CI	Confidence interval
CP	Conditional power
CRF	Case report form
C-SSRS	Columbia – Suicide Severity Rating Scale
CTMS	Type of deviation and severity
DBP	Diastolic blood pressure
DSM-5	Diagnostic and Statistical Manual of Mental Disorders, Fifth Edition
ECG	Electrocardiogram
eCRF	Electronic case report form
E/D	Early discontinuation
EDS	Excessive daytime sleepiness
EOT	End of treatment
FDA	Food and Drug Administration
GCP	Good Clinical Practice
ICF	Informed consent form
ICH	International Council for Harmonization of Technical Requirements for Pharmaceuticals for Human Use
INR	International normalized ratio
LOCF	Last observation carried forward
MedDRA	Medical Dictionary for Regulatory Activities
mITT	Modified Intent-to-Treat Set
NT1	Type 1 narcolepsy
NT2	Type 2 narcolepsy

Jazz Pharmaceuticals  
Statistical Analysis Plan - Protocol JZP258-406

OR	Odds ratio
ORE	Other reportable experience
PGIc	Patient global impression of change
PGIs	Patient global impression of severity
PT	Preferred term
SAE	Serious adverse event
SAP	Statistical analysis plan
SBP	Systolic blood pressure
SD	Standard deviation
SE	Standard error
SFU	Safety follow-up
SOC	System Organ Class
TEAE	Treatment-emergent adverse event
ULN	Upper limit of normal

## Appendix 1: Adverse Event Date Imputation Rules

Missing AE start dates will be imputed in the ADaM datasets for AE. However, missing AE end dates will not be imputed. After imputation based on rules below, if the imputed AE start date is after the AE end date, the start date will be imputed by the AE end date further.

### Incomplete Adverse Event Onset Date

If *year* is missing (or completely missing): set to the date of first dose.

If (*year* is present and *month* and *day* are missing) or (*year* and *day* are present and *month* is missing):

If *year* = year of first dose: set the date to the first dose date.

If *year* < year of first dose: set *month* and *day* to December 31st.

If *year* > year of first dose: set *month* and *day* to January 1st.

If *month* and *year* are present and *day* is missing:

If *year* = year of first dose, and:

If *month* = month of first dose: set *day* to day of first dose.

If *month* < month of first dose: set *day* to last day of *month*.

If *month* > month of first dose: set *day* to 1st day of *month*.

If *year* < year of first dose: set *day* to last day of month.

If *year* > year of first dose: set *day* to 1st day of month.

For all other cases: set to date of first dose.

## **Appendix 2: Prior/Concomitant Medications Date Imputation Rules**

### Incomplete Concomitant Medication Start Date

If *year* is missing (or completely missing): do not impute.

If (*year* is present and *month* and *day* are missing) or (*year* and *day* are present and *month* is missing):

Set *month* and day to January 1st.

If *year* and *month* are present and *day* is missing:

Set *day* to 1st day of month.

### Incomplete Concomitant Medication End Date

Do not impute if Ongoing Flag is checked.

If *year* is missing (or completely missing): do not impute.

If (*year* is present and *month* and *day* are missing) or (*year* and *day* are present and *month* is missing):

Set *month* and day to December 31st.

If *year* and *month* are present and *day* is missing:

Set *day* to last day of the month.

Signature Page for JZP258-406 SAP v3.0  
VV-CLIN-035379

Approval Task - Approval of Document Signing Verdict/Reason: I Approved This Document	 Data Sciences 05-Dec-2024 20:57:05 GMT+0000
Approval Task - Approval of Document Signing Verdict/Reason: I Approved This Document	 Data Sciences 05-Dec-2024 23:52:52 GMT+0000
Approval Task - Approval of Document Signing Verdict/Reason: I Approved This Document	 Medical Affairs 10-Dec-2024 16:08:20 GMT+0000

Signature Page for JZP258-406 SAP v3.0  
VV-CLIN-035379
